7. RESEARCH QUESTION AND OBJECTIVES

The study aims to address the following research question: Among US adults with migraine and prior use of opioids or barbiturates, how does the use of opioids and barbiturates change following rimegepant initiation? Specific study objectives include:

Primary Objective

1. To evaluate changes in opioid and barbiturate utilization patterns after the initiation of rimegepant.

Secondary Objectives

- 2. To describe the pre-treatment characteristics of new rimegepant users, including demographics, comorbid conditions, and prior medication use.
- 3. To evaluate changes in opioid and barbiturate utilization patterns after the initiation of rimegepant in the subset of individuals using at least one preventive treatment for migraine
- 4. To evaluate changes in opioid and barbiturate utilization patterns after the initiation of rimegepant in the subset of individuals with problematic opioid use (≥ 3 opioid prescriptions and/or morphine milligram equivalents [MME] above 75th percentile during pre-index period)

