8. RESEARCH METHODS

8.1. Study Design

This is a non-interventional, retrospective, observational, cohort study that will assess changes in opioid and barbiturate utilization after initiation of rimegepant among adults in the US. This study will analyze an administrative claims database (IQVIA PharMetrics® Plus) with information on

individuals in the US with commercial, managed Medicare, or managed Medicaid health plans. This database includes information captured in medical and pharmacy claims (e.g., dates of service, diagnosis codes, procedure codes, medications dispensed, demographics, health plan enrolment)⁴⁰.

This study aims to characterize, in a real-world setting, the use of opioids and barbiturates among individuals with migraine before and after initiating rimegepant. Individuals will be grouped according to their use of 5 medications prior to rimegepant initiation (index date): 1. opioids, 2. barbiturates (i.e., butalbital), 3. alprazolam, 4. rescue inhalers, or 5. statins. The latter three groups will be used as controls to represent medications intended for continuous use and episodic use.

Rimegepant is approved for both the acute treatment of migraine and the prevention of episodic migraine. For the acute treatment of migraine, rimegepant is taken as needed. For the prevention of episodic migraine, rimegepant is taken every other day. Since the same medication is approved for 2 indications, assumptions must be made about the intended use when analyzing real world data.

Rimegepant is commonly dispensed in packages of 8 tablets. When 2 packages (16 tablets) are dispensed, it is assumed that rimegepant is intended for the prevention of episodic migraine. When 1 package (8 tablets) are dispensed, it is assumed that rimegepant is intended for the acute treatment of migraine.

For each medication of interest, outcome measures will include the total number of prescriptions filled/dispensed, the total quantity dispensed (number of tablets or other medication units), the average dispensed per fill (calculated for opioids in MME and for butalbital and alprazolam in mg), the total duration of use (days supplied), and the proportion of individuals with discontinuation (defined as the absence of any prescription fill in after rimegepant initiation).

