8.2.1. Inclusion Criteria

Patients must meet all of the following inclusion criteria to be eligible for inclusion in the study:

- 1. Have an index ("first") prescription fill for rimegepant between March 1, 2020, and October 1, 2022; the date of this index fill defines the index date
 - a. The end date of cohort eligibility is 6 months prior to the end of data availability to ensure sufficient follow-up for all patients prior to the end of data availability. For the 12-month sensitivity analysis, the end of cohort eligibility will be April 1, 2022.
- 2. Have an index fill quantity for rimegepant of 8 tablets (ie, intended use for acute treatment of migraine).
- 3. Have ≥ 180 days of rimegepant use from index date to last fill date +30 days
 - a. The period of rimegepant use is measured as the number of days from the index date, or first observed rimegepant fill, to the last observed rimegepant fill date +30 days.
- 4. Be \geq 18 years of age on the index date

- 5. Have ≥180 days of continuous enrollment in commercial health plans with both medical and pharmacy benefits prior to and following the index date, defined as the pre-index period and post-index period, respectively
- 6. Have a diagnosis of "migraine" (ICD-10-CM code: G43.xx) at *any point* during the pre- or post-index periodsHave ≥1 prescription fill during the pre-index period for one of the following drugs of interest: opioids, barbiturates (butalbital), alprazolam, rescue inhalers, or statins

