Any injury	Baseline characteristic	Medical claims	Binary (ICD-10)	
Any surgical procedure	Baseline characteristic	Medical claims	Binary (CPT)	
	Outcon	ne Measures		
Total number of fills dispensed	Outcome measure	Rx claims	Count	
Total quantity dispensed	Outcome measure	Rx claims	Count	
Average dose (MME or mg) within time period	Outcome measure	Calculated	Continuous (calculated): Mean/SD	
Total duration of use (days)	Outcome measure	Calculated	Continuous (calculated)	
Discontinuation	Outcome measure	Rx claims	Binary (no prescription fills during post-index period)	
Additional measures for opioid use group:				
Type of opioid used	Outcome measure	Rx claims	Binary	
Total number of Rx opioid agents used (mean)	Outcome measure	Rx claims	Count	
Total number of Rx opioid agents used	Outcome measure	Rx claims	Categorical: $1, 2, \ge 3$	

CGRP: Calcitonin Gene-Related Peptide; CPT: Current Procedural Terminology; HCPCS: Healthcare Common Procedural Coding System; ICD10: International Classification of Diseases, 10th Revision; MME: Morphine Milligram Equivalents; NSAIDs: Nonsteroidal anti-inflammatory drugs; Rx: Prescription; SD: Standard Deviation

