8.7. Data Analysis

The workflow below will be applied to conduct data analysis.

- 1. First, all individuals who meet all study eligibility criteria (study population) will be identified.
- 2. Second, all data for the study population will be extracted from the study database into an analytical file that will be used for all subsequent analyses.
- 3. Third, all required study variables will be identified or calculated in the study population.

The Center for Center for Medicare & Medicaid Services (CMS) Opioid Oral MME Conversion Factors Table (available at the US department of Health and Human Services portal) will be used to standardize opioid dose measurements in MME (ie, for each prescription, the daily dose will be multiplied by the corresponding opioid conversion factor and then divided by days supplied; MMEs will be summed across all opioid prescriptions).

- 4. Fourth, all required subgroups will be created in the study population.
- 5. Fifth, study outcomes will be summarized across study subgroups, which are determined by the pharmaceutical form of each medication as summarized in the table below:

Table 2. Study subgroups

	Opioids	Barbiturates	Alprazolam	Rescue Inhalers	Statins
Number of Rx fills	X	X	X	X	X
(mean, SD, % change)					
Tablets/quantities dispensed	X	X	X	X	X
(mean, SD, % change)					
Milligrams dispensed		X	X		
(mean, SD, % change)					
Morphine milliequivalents (MME)	X				
(mean, SD, % change)					

Days supplied	X	X	X	X	X
(mean, SD, % change)					
Discontinuation in post-index	X	X	X	X	X
(mean, SD, % change)					

Subgroups vary according to the dosage form of each medication. Rx: prescription

6. Sixth, statistical comparisons will be conducted according to the Statistical Analysis Plan, described below.

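### A patient who used only opioids or only butalbital before index and switches to the other counts as discontinued, and on the natural reading the new fills enter no planned outcome

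*Protocol*

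**What the plan says.** Section 7 asks, in adults with prior use of either class, "how does the use of opioids and barbiturates change following rimegepant initiation". Section 8.1 sets the groups: "Individuals will be grouped according to their use of 5 medications prior to rimegepant initiation", the five being opioids, butalbital, alprazolam, rescue inhalers and statins. Entry under section 8.2.1 needs at least one "prescription fill during the pre-index period for one of the following drugs of interest".

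Outcomes are defined per drug. Section 8.1 says "For each medication of interest, outcome measures will include the total number of prescriptions filled/dispensed", and then lists quantity, average dose, days supplied and discontinuation, the last "defined as the absence of any prescription fill in after rimegepant initiation". Table 1 in section 8.3 repeats discontinuation as "Binary (no prescription fills during post-index period" and does not name the drug. Section 8.7 says "study outcomes will be summarized across study subgroups, which are determined by the pharmaceutical form of each medication". Table 2 has one column per drug, with no combined opioid-or-barbiturate column and no row for use of a different drug. Section 8.7.1 describes baseline characteristics, and presents the preventive-treatment subgroup, by medication use group.

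The protocol does not say whether the groups may overlap, or in words that a group's outcomes count only its own drug. The limitations in section 8.9 do not mention movement between the two classes.

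**The concern.** Section 6 describes both classes as risking dependence, contributing to medication overuse headache and progression to chronic migraine, and advised against by guidelines. Section 8.1 names them together as suboptimal migraine drugs. Moving from one to the other is therefore not the reduction that the research question is about.

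With groups fixed by pre-index use and results kept drug by drug, such a move lowers use in the group the patient belongs to and raises it in a group the patient does not belong to. Both groups could then report a decline larger than the fall in opioid-or-barbiturate use as a whole. The alprazolam, inhaler and statin controls cannot show this, because they follow other drugs.

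**Working it through.** No figure in the protocol bears on this point, so there is none to reproduce. The check is a reading of the definitions, followed by an illustration.

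**Step 1. Is discontinuation specific to the group's own drug?** The text does not say so, but two points make any other reading unworkable.
- Inclusion criterion 3 needs at least 180 days from index to the last rimegepant fill plus 30 days. The last fill is therefore at least 180 − 30 = 150 days after index, and every patient has a rimegepant fill after initiation. Taken literally, the section 8.1 definition could never be met, so it must refer to the drug of interest.
- If opioid discontinuation were computed in the whole cohort, every patient who entered on statins or inhalers alone and filled no opioid after index would count as having discontinued opioids. The outcome makes sense only among prior users of that drug.

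**Step 2. Follow the possible patients.**

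| Pre-index fills | Post-index fills | Opioid group | Barbiturate group |
|---|---|---|---|
| Opioid only | Butalbital only | Discontinued | Not a member; new fills uncounted |
| Butalbital only | Opioid only | Not a member; new fills uncounted | Discontinued |
| Both | Butalbital only, increased | Discontinued | Increase visible, if groups overlap |

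**Step 3. Direction.** A single-class user has no pre-index fills of the other class, so any post-index fills of it can only add to post-index use. The combined reduction can equal the drug-specific one or be smaller, never larger.

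**Step 4. Illustration.** Let D be the share of a single-class group with no post-index fill of its own drug, and s the share of those stoppers who newly fill the other class. Both are assumptions; the protocol gives neither. The share free of both is D × (1 − s), and the gap is D × s. With D = 40%:

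| s | Free of both | Gap (percentage points) |
|---|---|---|
| 0% | 40% | 0 |
| 5% | 0.40 × 0.95 = 38% | 2 |
| 10% | 0.40 × 0.90 = 36% | 4 |
| 20% | 0.40 × 0.80 = 32% | 8 |
| 30% | 0.40 × 0.70 = 28% | 12 |

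Over D = 20% to 50% and s = 5% to 30%, the gap runs from 0.20 × 0.05 = 1 point to 0.50 × 0.30 = 15 points.

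The upper end is probably generous. At D = 40%, s = 30% means that 12% of the whole group newly starts the other class within 180 days. Section 6 gives 6% and 12.8% of survey respondents using barbiturate-containing analgesics, but those are different populations and current use, not new starts.

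**The case against.** The strongest reply is that the restriction to a group's own drug is inferred. Section 8.1 speaks of each medication of interest without limiting it to prior users. Section 8.6 places the operational logic in a data dictionary, and Annex 1 also lists table shells; neither is at hand. If fills and quantity were computed in the whole cohort, new fills would enter the other drug's totals. That stands as a caution for those outcomes, and is why the rule should be written down. It does not rescue discontinuation, for the reasons in step 1.

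A reader might infer that switching is never visible, or that it always biases the result. The protocol does not support either. The groups are not declared mutually exclusive, so a patient who filled both classes before index could show higher butalbital use in the barbiturate group. Section 6 notes that butalbital is sometimes combined with codeine, so some such fills might also count as opioid. Without switching there is no bias.

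It can also be said that drug-by-drug reporting is a legitimate reading of utilization patterns, that fills are counted for any reason (section 8.4), and that the protocol disclaims causal conclusions (sections 8.1 and 8.9). All true: a new butalbital fill need not replace an opioid. But the question is how use of the two classes changes, and the drug-specific outcomes leave out one part of that change for single-class users, whatever its cause.

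**Conclusion.** The point holds for patients with pre-index fills of only one of the two classes. On the natural reading, those who stop it and newly start the other are counted as discontinued and their new fills reach no planned outcome. Whenever this happens, the drug-specific results overstate the reduction in opioid-or-barbiturate use.

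The size cannot be derived from the protocol. Under the assumptions of 40% drug-specific discontinuation and 5% to 30% of stoppers switching, the overstatement is 2 to 12 percentage points; it is zero without switching. The conclusion rests on each group's outcomes following its own drug, which is strongly implied but not stated. It does not show that substitution is common, or that the planned results are wrong by any particular amount. This should be corrected, but it does not invalidate the drug-specific analyses.

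**What to change.** 1. State in sections 8.1 and 8.7 whether the groups may overlap, and that each group's outcomes count its own drug. Say which class a butalbital-codeine fill belongs to.
2. In everyone with at least one pre-index opioid or butalbital fill, add two outcomes: fills of either class per period, and combined discontinuation, meaning no fill of either class in the post-index period.
3. Among patients with pre-index fills of only one class, report the percentage with a first fill of the other class after index, separately for each class.
4. Keep MME and milligrams separate; the two doses should not be pooled.

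The cost is a pooled cohort and a few extra outputs from data already extracted. The abstract says the analyses were completed in 2024 and a manuscript was accepted in 2025, so these should be labelled as added analyses. The final study report is planned for 1 March 2026 and could carry them. The reported reduction may become less favourable.

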8.4. Data Sources

This study will use the IQVIA PharMetrics® Plus longitudinal health plan database with medical and pharmacy claims adjudicated by third-party payers managing commercial health plans. Individuals in this database are a geographically representative sample of the US commercially insured population⁴⁰. The database contains information on patient demographics, plan enrollment, inpatient and outpatient medical claims, and outpatient pharmacy claims. These data were used as presented by the data source, without recoding. The primary outcomes in this study are based on observed pharmacy fills for the medications of interest (opioids, barbiturates, alprazolam, rescue inhalers, or statins) for any reason, so minimal interpretation or reliance on clinical coding accuracy is required. The data are de-identified and compliant with the Health Insurance Portability and Accountability Act (HIPPA)⁴⁰. This data source has been used extensively in pharmacoepidemiology research⁴⁵⁻⁴⁹.

8.5. Study Size

Since this is a retrospective study of existing and commercially available data, no formal sample size calculation was performed. The study database includes 52,591,063 individuals. It is estimated that 45,051 (0.86%) have an eligible first prescription for rimegepant and 4,049 (0.0077%) meet all eligibility criteria.

8.6. Data Management

All data for this study will be extracted from the IQVIA PharMetrics® Plus longitudinal health plan database. IQVIA is the data vendor and data store, providing access to a structured, de-identified dataset of adjudicated medical and pharmacy claims from a geographically representative sample of individuals with commercial, managed Medicare, or managed Medicaid health insurance in the United States.

Data will be obtained directly from IQVIA by Pfizer's Real World Evidence (RWE) team under an active data use license. The extraction process will follow Pfizer's standard operating procedures for secondary data studies. The RWE team will submit a formal data extraction request to IQVIA, specifying all required variables, inclusion and exclusion criteria, and the study timeframe. The data will be delivered in a secure, structured format (e.g., CSV or SAS datasets) and transferred to Pfizer's secure analytics environment for processing and analysis. The data extract will be limited to patients meeting the study's inclusion and exclusion criteria (e.g., adults with a diagnosis of migraine, first prescription fill for rimegepant between March 1, 2020, and October 1, 2022, continuous enrollment, etc.) and will occur once.

The technical specifications for the data extract—including all variable definitions, coding, and inclusion/exclusion parameters—are detailed in the study's data dictionary (see ANNEX 1. LIST OF STANDALONE DOCUMENTS). It provides detailed definitions, coding algorithms, and operational logic for all variables, exposures, outcomes, and covariates used in the study. This includes:

- Demographics: Definitions and coding for age, sex, and region.
- Comorbidities: Algorithms and ICD-10 codes for identifying chronic pain, migraine, and other relevant conditions.
- Medication Exposures: Lists of generic names, NDC/HCPCS codes, and logic for identifying study medications (e.g., opioids, barbiturates, migraine preventives, rescue inhalers, statins).
- Surgical and Injury Variables: CPT and ICD-10 code mappings for identifying major surgical procedures and injuries.
- Outcome Measures: Algorithms for calculating prescription fills, quantity dispensed, average dose (MME or mg), duration of use, and discontinuation.
- Operational Definitions: Clear instructions for how each variable is derived from claims data, including data sources (pharmacy or medical claims) and measurement periods.

All data are de-identified and compliant with the Health Insurance Portability and Accountability Act (HIPAA). Data management, storage, and analysis will be performed exclusively by authorized Pfizer personnel in accordance with internal quality standards and regulatory requirements.

8.7. Data Analysis

The workflow below will be applied to conduct data analysis.

- 1. First, all individuals who meet all study eligibility criteria (study population) will be identified.
- 2. Second, all data for the study population will be extracted from the study database into an analytical file that will be used for all subsequent analyses.
- 3. Third, all required study variables will be identified or calculated in the study population.

The Center for Center for Medicare & Medicaid Services (CMS) Opioid Oral MME Conversion Factors Table (available at the US department of Health and Human Services portal) will be used to standardize opioid dose measurements in MME (ie, for each prescription, the daily dose will be multiplied by the corresponding opioid conversion factor and then divided by days supplied; MMEs will be summed across all opioid prescriptions).

- 4. Fourth, all required subgroups will be created in the study population.
- 5. Fifth, study outcomes will be summarized across study subgroups, which are determined by the pharmaceutical form of each medication as summarized in the table below:

Table 2. Study subgroups

	Opioids	Barbiturates	Alprazolam	Rescue Inhalers	Statins
Number of Rx fills	X	X	X	X	X
(mean, SD, % change)					
Tablets/quantities dispensed	X	X	X	X	X
(mean, SD, % change)					
Milligrams dispensed		X	X		
(mean, SD, % change)					
Morphine milliequivalents (MME)	X				
(mean, SD, % change)					

Days supplied	X	X	X	X	X
(mean, SD, % change)					
Discontinuation in post-index	X	X	X	X	X
(mean, SD, % change)					

Subgroups vary according to the dosage form of each medication. Rx: prescription

6. Sixth, statistical comparisons will be conducted according to the Statistical Analysis Plan, described below.

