Variables: The primary exposure is initiation of rimegepant, defined by the first prescription fill between March 1, 2020, and October 1, 2022. Outcomes include changes in opioid and barbiturate utilization patterns before and after rimegepant initiation, measured by prescription fills, quantity dispensed, average dose, duration of use, and discontinuation. Key covariates are demographic and clinical characteristics (age, sex, region, comorbidities, chronic pain, prior preventive treatments) assessed during the baseline period.

Data sources: This study will analyze the IQVIA PharMetrics[®] Plus longitudinal health plan database, which includes anonymized, medical and pharmacy claims from closed-network, third-party payers in the US. This database includes commercial, managed Medicare, and managed Medicaid health plans.

Study size: The study database includes 52,591,063 individuals. It is estimated that 45,051 (0.86%) have an eligible first prescription for rimegepant and 4,049 (0.0077%) meet all eligibility criteria.

Data analysis: Number of fills and quantity dispensed (in MMEs for opioids and milligrams for barbiturates) will be assessed in the 180 days before and after the index fill for rimegepant. Changes in key outcomes will be analyzed using generalized linear mixed models adjusted for age, sex, region, chronic pain, comorbidities, and use of preventive treatment for migraine. Subgroup analyses will be conducted among individuals using ≥ 1 preventive treatment and individuals with problematic opioid use (≥ 3 fills or MMEs above 75th percentile).

Milestones: This study was initiated in 2023. Analyses were completed in 2024. A manuscript based on this study was accepted for publication in 2025.

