8.7.1. Statistical analysis plan

- 1. Among each medication use group, a report with descriptive statistics of the demographic and clinical baseline characteristics as well as medication use prior to rimegepant will be created.
- 2. Next, a patient-level dataset containing crude counts of the five utilization outcome measures for each 30-day window (W1-W12) of the pre- and post-index periods will be created.
- 3. To measure changes in utilization outcome measures across the pre-index to post-index period, two aggregated measures for each outcome based on time during the pre- (W1-W6) or post-index (W7-W12) period will be created. Using these aggregate measures, the pre and post-index mean outcome values and determine the percent change (%Δ) will be presented.
- 4. In order to determine the association between rimegepant initiation and reduction of other acute treatments, a generalized linear mixed models for each outcome will be applied. Mixed effects models account for within-person correlation due to the repeated measurement of outcomes over time in longitudinal studies. The main independent (exposure) variable will be a binary indicator of time during the pre-index period (0) vs. post-index period (1). For modeling the continuous and count outcomes—number of fills, quantity dispensed, average dose, and duration of use—first the distribution of each utilization outcome measure within the dataset will be determined in order to specify the appropriate distributions and link functions for their mixed model. The discontinuation outcome is a binary outcome, observed at one point in time. Hence, a logistic regression model to examine any association to rimegepant initiation will be applied. For each model, for pre-index demographic and clinical characteristics, including age, sex, region, presence of any chronic pain (migraine or non-migraine), Elixhauser weighted index, and pre-index use of any prevention agent will be adjusted.
- 5. To determine the robustness of the outcome measures and association estimates, two subgroups and two sensitivity analyses will be performed as described below. The sensitivity analyses only apply to the total cohort, and not the additional subgroups.
 - a) Subgroup analysis #1: Identify all individuals from the total cohort with use of ≥ 1 prevention agent during the pre-index period, presented by medication use group.

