- b) Subgroup analysis #2: Identify individuals form the opioid use group having potentially problematic opioid use. This subgroup is a composite of problematic opioid use defined in two ways. Patients meeting either measurement definition will be included.
 - i. The first method will identify individuals in the cohort with ≥ 3 opioid prescriptions during the pre-index period.
- 6. The second method will calculate quartiles of opioid dose in MMEs and identifies individuals within the fourth quartile (76th to 100th percentile) during the pre-index period.
 - c) Sensitivity analysis #1: Increase the duration of the pre-index and post-index periods from 180 days each to 360 days each.
 - d) Sensitivity analysis #2: Exclude all patients having a major surgical procedure or injury diagnosis at any point during the study period.

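### The protocol's MME formula divides an already daily dose by days supplied, so as written it yields neither a total nor a daily MME and penalises longer opioid fills.

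*Protocol*

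**What the plan says.** Section 8.7, step 3, standardises opioid doses with a published conversion table. For each prescription, "the daily dose will be multiplied by the corresponding opioid conversion factor and then divided by days supplied"; after that, "MMEs will be summed across all opioid prescriptions". No other formula for MME appears in the protocol.

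Elsewhere the same measure is described in three further ways:

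- Abstract, data analysis: "quantity dispensed (in MMEs for opioids and milligrams for barbiturates", that is, a total.
- Section 8.1: "the average dispensed per fill (calculated for opioids in MME and for butalbital and alprazolam in mg", that is, a mean over fills.
- Section 8.3, Table 1: "Average dose (MME or mg) within time period", that is, a mean over a period.

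MME has its own opioid row in Table 2. Dose is also one of the four modelled continuous or count outcomes in Section 8.7.1, step 4: "number of fills, quantity dispensed, average dose, and duration of use". In subgroup analysis #2 the second route to problematic use is to "calculate quartiles of opioid dose in MMEs and identifies individuals within the fourth quartile". Section 8.6 says that a data dictionary holds the outcome algorithms. Annex 1 lists it as version 3 of 15 November 2023, but it is not among the documents at hand.

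**The concern.** A daily dose multiplied by a conversion factor is in MME per day. Dividing it by days supplied gives MME per day squared, which has no interpretation as exposure. The distortion is not a constant that cancels in a before/after percentage: it depends on fill length, and fill length may itself change if opioid use changes.

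MME is the only opioid dose measure under the primary objective, and it is one of two routes into the subgroup of objective 4. If the sentence is followed literally, a fall in opioid exposure can appear as a rise. The fourth quartile, meant to capture the heaviest users, would favour patients with short courses.

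**Working it through.** **Inputs.** The formula and the summation rule come from Section 8.7, step 3. The protocol gives no MME value or worked example, so there is no stated figure to reproduce. The 20 MME/day and the fill lengths below are assumptions chosen for illustration.

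**Algebra.** Let s = strength per unit, q = units dispensed, D = days supplied and CF = conversion factor.

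- Total MME = s × q × CF
- Daily MME = (s × q / D) × CF
- As written = [(s × q / D) × CF] / D = daily MME / D = total MME / D²

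**One fill at an assumed 20 MME/day.**

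| D (days) | Daily MME | Total MME | As written |
|---|---|---|---|
| 1 | 20 | 20 | 20 |
| 3 | 20 | 60 | 6.67 |
| 5 | 20 | 100 | 4.0 |
| 10 | 20 | 200 | 2.0 |
| 30 | 20 | 600 | 0.67 |
| 90 | 20 | 1800 | 0.22 |

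The 30-day fill is 30-fold low as a daily MME (20 / 0.667) and 900-fold low as a total (600 / 0.667). The 5-day fill scores 6 times the 30-day fill (4.0 / 0.667), although its total is one sixth (100 / 600).

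**Ranking of patients.** Six 30-day fills at 20 MME/day total 6 × 600 = 3600 MME and score 6 × 20/30 = 4.0. One 3-day fill totals 60 MME and scores 20/3 = 6.67. The order is reversed.

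**Direction of change.** Take one 30-day fill before index and one 5-day fill after, both at 20 MME/day.

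- Total MME: (100 − 600) / 600 = −83%
- Daily MME: (20 − 20) / 20 = 0%
- As written: (4.0 − 0.667) / 0.667 = +500%

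**Top quartile.** I simulated 20,000 patients under each of two assumed mixes of 3-to-10-day and 30-day fills, with 1 + Poisson(1.5) fills per patient and log-normal daily doses (median 25 MME). Of the true top quartile by total MME, 20% and 24% stayed in the top quartile under the written formula. In the composite subgroup about 11% of patients changed status under either mix, because the route through three or more prescriptions does not use MME. These percentages depend on the assumed mixes and are not estimates for this cohort.

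**The case against.** **It may be a slip of wording.** Section 8.9, item 8, says that pharmacy claims carry little beyond drug name, quantity and strength. A daily dose therefore probably has to be derived, and dividing the total dispensed by days supplied is the natural way. The phrase for daily dose may simply stand for total dose. This is plausible, but it does not settle the matter. The rule would then sum MME per day over successive fills: six 30-day fills at 20 MME/day would give 120, which is neither the total of 3600 nor the average of 20. The four descriptions would still disagree.

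**The data dictionary may govern.** It predates the protocol (12 November 2025), and the abstract says that analyses were completed in 2024. A reader might infer that the reported MME results are wrong. The documents do not show that. They show a wrong sentence; the effect on results is conditional on the code. This part of the objection stands.

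**Short fills are not inflated.** A reader might infer that they are. For D ≥ 1 the written value never exceeds the true daily or total MME. A 1-day fill is unchanged and every longer fill shrinks, so short fills gain only relative to long ones.

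**Patients who stop are not shown to be dropped.** An average per fill has no value when there is no fill, and a reader might infer that the post-index mean omits those who stopped. No section says so, and Table 1's average within a period can be read as zero for them.

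**The reach is limited.** No single primary outcome is named. Fills, tablet quantity, days supplied and discontinuation do not use MME. Problematic use is an either/or definition, and its other limb counts prescriptions.

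**Conclusion.** The MME definition in Section 8.7 is wrong as worded, and nothing else in the protocol corrects it. It gives total MME/D², which agrees with none of the descriptions in the abstract, Section 8.1 or Table 1. The algebra needs no assumption beyond taking the sentence literally. The sizes quoted rest on the assumed 20 MME/day and fill lengths: a 900-fold understatement of a 30-day total, and +500% in place of −83% for one constructed patient. The direction of any error in the cohort depends on its mix of days supplied, which is not given.

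The point covers the opioid MME outcome and the fourth-quartile limb of subgroup #2 only. It does not establish that completed results are in error, and it is no reason to remove average dose from the modelled outcomes. It should be corrected and checked before the final study report, because a rule that can reverse the sign of the dose outcome should not stand in the protocol.

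**What to change.** Replace the parenthesis in Section 8.7, step 3, with: total MME per prescription = strength per unit × quantity dispensed × conversion factor; total MME per period = sum over prescriptions, 0 if there is no fill; if an average daily dose is reported, divide that sum once by a stated number of days.

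Then:

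- Align the abstract, Section 8.1, Table 1 and Section 8.7 with this definition.
- State which MME measure defines the fourth quartile in subgroup #2.
- Confirm, and state, which formula the data dictionary and the programs used.
- If it was the written one, rerun the MME results and subgroup #2 before the final study report, planned for 01 March 2026.

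The cost is one replaced sentence, matching edits in three other places and a code check. Any rerun would use data already held.
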